Patient Health Questionnaire-9 (PHQ-9): The PHQ-9 is a 9-item depression module in the Patient Health Questionnaire (a self-administered diagnostic instrument for common mental disorders) which is part of the Primary Care Evaluation of Mental Disorders (PRIME-MD) suite of evaluation tools.⁵⁹ The PHQ-9 will be used to measure depressive symptom severity. The items align to the DSM-IV diagnostic criteria for depressive disorders. The PSQ-9 is widely used to screen for depression within VA. Key variable: PHQ-9 total score

Generalized Anxiety Disorder-7 (GAD-7): The GAD-7 scale is a component of the PRIME-MD suite of evaluation tools.⁵⁹ The GAD-7 was initially developed for evaluation of Generalized Anxiety Disorder (GAD), and has also proved useful in screening for other DSM-IV Axis I anxiety disorders. The GAD-7 is a 7-item scale (scores range from 0 to 27), with a cut off score of ≥ 10 yielding both sensitivity and specificity above .80 for GAD, and specificity above .80 for Panic, Social Anxiety and PTSD. The GAD-7 is less sensitive in screening for panic (.74), social anxiety (.72) and PTSD (.66). A more robust measure of PTSD will be used in the current study as described above PCL-5 and M.I.N.I.). Key Variable: GAD-7 total score.

3.5b. Attrition and Adherence Monitoring Measures (Aim 1)

Table 8: Study variables and measurements gathered during the intervention		Session				
Variable	Measurement Instrument	1	2	3	4	5
Adherence Monitoring Measures (Aim 1)						
Treatment attendance	Attendance log	X	X	X	X	X
Adherence to bedtime and rise time and other recommendations	Daily sleep dairies with electronic date/time stamp	X	X	X	X	X
Intervention Process measures						
Components of psychological flexibility	Acceptance and Action Questionnaire-II (AAQ-II) ⁷⁰	X				X
Treatment Outcome Expectations	Credibility/Expectancy Questionnaire (CEQ) ⁷¹	X				X
Beliefs and attitudes about sleep	DBAS-10 ⁷²	X				X
Sleep hygiene habits	Sleep Hygiene Index ⁷³	X				X

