Treatment attendance: One of the main study outcomes will be rates of treatment completion versus dropout. To measure this construct, we will track attendance at each session, and will consider an individual to have "completed" treatment if they attend 5 60-minute sessions with the interventionist. A dichotomous variable will be computed to indicate whether the treatment program was completed or not. While not one of the main study outcomes, we will also monitor rates of cancellations/rescheduled appointments. As described above, the process for maintaining participants in treatment will be standardized across the two intervention programs. Key variable: treatment completion versus dropout.

Daily sleep diaries with electronic date/time stamp: Participants will complete an expanded version of the baseline sleep diary during the intervention portion of the study. The diary will be completed each morning, and an electronic date/time stamp will be used to document the time at which the diary was completed. This will increase the likelihood that the participant will complete the diary daily rather than completing it on the day of the intervention session. The diaries will be reviewed in detail each week by the interventionist and recommendations will be based on the sleep diary. In addition, this will be used as a measure of treatment adherence to the behavioral recommendations using the process developed by Matthews et al.¹⁸ Each week the interventionist will make recommendations for behavior changes, and we will use the sleep diary to calculate the mean number of minutes the participant goes to bed in advance of their scheduled bedtime and the mean number of minutes they get up later than their scheduled rise time (note that going to bed later than the assigned time or getting up earlier than the assigned time is consistent with the recommendations and is not considered non-adherence). We will then compute the mean minutes of deviation for each participant. We will also compare rates of adherence to other between-session activities, and a percent of days the activity was conducted will be computed for each participant (note that for some participants, recommendations may not be made in some weeks). Key process variables: Minutes of deviation from assigned bedtime and rise times; Days per week participant adhered (within 15 minutes) to assigned bedtime, rise time and time in bed.

3.5c. Intervention Process Measures

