Intervention process measures will be completed by randomized participants at the end of the first treatment and final (fifth) treatment sessions. We have selected this approach since some measures cannot be completed until the individual has a basic understanding of the treatment program she will receive.

Acceptance and Action Questionnaire-II (AAQ-II):⁷⁰ The AAQ-II is a 7-item questionnaire to assess experiential avoidance as conceptualized in ACT (higher scores suggest more avoidance). The AAQ-II has acceptable psychometric properties. In a recent study of 376 adults with depression or anxiety symptoms, using a unidimensional item response theory (IRT) model, the AAQ-II was found to be a unidimensional measure of experiential avoidance with satisfactory reliability. Key variable: AAQ-II total score

Dysfunctional Beliefs and Attitudes about Sleep – 10 item (DBAS-10):⁷² The DBAS-10 is an abbreviated version of the original 28-item DBAS examining beliefs about the immediate and long-term negative consequences of insomnia as well as beliefs about the need for control over insomnia. This 10-item version has been shown to be well correlated ($r=0.83$) with the full scale and sensitive to cognitive changes resulting from cognitive-behavioral therapy for insomnia. Key variables: DBAS total score

Sleep Hygiene Index (SHI):⁷³ The 13-item sleep hygiene index is based on diagnostic criteria for inadequate sleep hygiene, and has superior reliability compared to other (typically longer) sleep hygiene questionnaires (Chronbach's $\alpha=0.66$). This measure will be used to identify sleep hygiene related behaviors, including the use of alcohol, caffeine and tobacco within 4 hours of bedtime. Key variable: SHI total score

Credibility/expectancy questionnaire (CEQ):⁷¹ The CEQ is a 6-item questionnaire used both at the beginning and end of treatment. *This questionnaire will be administered at the end of the first treatment session and again at the end of the final treatment session in both the ABC-I and CBT-I groups.* Since this measure cannot be used until the individual understands the type of treatment she will receive, it will not be assessed until after session 1 when information about the treatment is available. The post-treatment items will be administered at the end of the final treatment session as well (session 5). Differences in scores between the ABC-I and CBT-I groups will be explored. Key variable: CEQ total scores at the beginning and end of treatment

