3.6b. Cognitive-Behavioral Therapy for Insomnia (CBT-I) Program: The ABC-I program will be compared to CBT-I, provided in the same format to control for non-specific aspects of the ABC-I program and to evaluate the comparative effectiveness of the two treatments (see **Table 10**). Participants will maintain the same daily sleep diary throughout the treatment. The sleep restriction, stimulus control and sleep hygiene components will be analogous to what is provided within the ABC-I. The CBT-I program will also involve 5 60-minute meetings with the interventionist. In place of mindfulness and ACT-based exercises, cognitive therapy exercises and techniques will be utilized.

Table 10: ABC-I and CBT-I treatments: Session-by-session content, activities and homework

	Topics covered	Session activities	Homework
Session 1	ABC-I: Learning How to Surf: An introduction to the ABC of Insomnia program (sleep education, sleep hygiene and stimulus control + ACT; see Appendix 3)		
	
 Enhance motivation to adhere to behavioral prescriptions (values) Futility of trying to control sleep Sleep education: insomnia (3P model), sleep stages and macrostructure among women Lifestyle habits that enhance or hinder sleep among women Introduce and explain daily sleep diary 	
 Insomnia and what is important to you Metaphors: Chinese finger trap; surfing Leaves on a stream exercise Action plan: sleep hygiene changes; stimulus control 	
 Draw life with and without insomnia Implement action plan (sleep hygiene practices) Daily sleep diary
Session 2	CBT-I: Getting Started with CBT-I (sleep education, sleep hygiene and stimulus control)		
	
 Sleep education: sleep regulation, insomnia (3P model), sleep stages and macrostructure Introduce stimulus control concepts Lifestyle habits that enhance or hinder sleep Introduce and explain daily sleep diary 	
 Discuss classical conditioning and insomnia Action plan: sleep hygiene changes; stimulus control 	
 Implement action plan (sleep hygiene practices) Detailed daily sleep diary
Session 3	ABC-I: Renovating your Home (sleep restriction therapy + ACT)		

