3.8. Data analysis plan

3.8a. Overview: Below we provide an overview of the study design considerations, and the analysis plan for each aim. We first present the approach for Aim 1, which involves traditional between-groups comparisons. Given the comparative effective approach required by Aims 2 and 3, we discuss these separately, and provide details regarding the structure of hypothesis testing for this method. In particular, we focus on the null hypothesis testing procedure and the determination of the clinically-meaningful effects (i.e., delta or δ) to be considered with respect to non-inferiority.

3.8b. Study Design Considerations: The equivalency of the two treatment groups at baseline is produced by the random assignment to groups. Randomization (combined with the ITT analysis strategy) should produce groups that differ only by chance with respect not only to factors related to study outcomes, and also to the outcomes themselves. Nevertheless, the adequacy of the randomization will be assessed by comparing the groups across outcomes measured at baseline. We will use a stratification based on hours of sleep reported on the postal survey (>6 versus ≤ 6 hours) to assign participants to strata for randomization. We have chosen stratified randomization to further increase the likelihood that the groups will be equivalent at baseline. The inclusion of covariates in such a situation would not be for the purpose of ensuring the comparability of the groups (because that comparability is created via randomization), but covariates may be used to enhance statistical power by reducing error variance.

We anticipate that some participants will not complete the intervention; however, we will continue to collect post-treatment and 3-month follow-up data, regardless of whether they complete the intervention program. Participants will be offered monetary incentives for providing post-treatment and follow-up assessments, regardless of whether they complete the intervention program to which they were assigned. We anticipate this will maximize the completeness of data; however, some data loss is unavoidable. In our recent study of older Veterans, we were able to obtain follow-up data for up to one year in 90% of randomized participants.

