Sample Size Calculations: To assess the power for Aim 1, we considered preliminary data gathered using the proposed intervention and previously published research. To estimate the power to compare dropout rates for each of the two groups, we used our preliminary data and published studies of ACT-based interventions and CBT-I.^{17;18;84-87} Based on those sources, we conservatively anticipate the dropout rate for ABC-I will be 22% compared to 45% for CBT-I. **Table 11** shows the required sample size to detect this difference (n=178) and other potential differences. The rows show dropout rates for ABC-I ranging from 16% to 28%, and the columns show dropout rates for CBT-I, ranging from 39% to 51%. Each cell shows the total N (for the two groups combined). The current study would need 148 subjects (74 per group) to have 80% power to detect a difference in dropout rates as found in the previous research.

Aim 1 also addresses differences between ABC-I and CBT-I in adherence to sleep restriction and stimulus control recommendations. Again, based on previously-published studies^{17;18;84-87} and our own preliminary data, we estimate that participants who complete the CBT-I intervention will deviate from their recommended bed time by an average of 29 minutes (SD=36 minutes) per night, while participants in the ABC-I program will deviate from their recommended bed time by an average of 9 minutes (SD=19 minutes). To detect a difference of this size with 80% power, we would require a total of 66 participants (33 per group). Similarly, we anticipate that individuals in the CBT-I group will deviate from their recommended rise time by 36 minutes (SD=40 minutes), while individuals in the ABC-I program will deviate from their recommended rise time by only 6 minutes (SD=14 minutes). To detect a difference of this magnitude with 80% power would require a total of 32 observations (16 per group). Using the proposed sample size required to detect a difference in dropout rates (n=148) we will have ample statistical power to detect differences in adherence.

Table 11: Sample size to detect differential dropout rates between CBT-I and ABC-I. N=148 (74 per group) is adequate to measure the expected difference. Other measurable differences with N=148 are shown in **bold**.

ABC-I Dropout rate	CBT-I dropout rate						
	39%	41%	43%	45%	47%	49%	51%
16%	134	116	102	90	82	74	66
18%	162	138	120	106	94	84	76
20%	200	168	144	124	108	96	86
22%	252	206	174	148	128	112	98

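### AAQ-II, DBAS-10 and Sleep Hygiene Index are given only at the end of sessions 1 and 5, so they lack a pre-treatment score and their end score comes essentially from completers

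*Combined protocol and SAP*

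**What the plan says.** **Timing.** Section 3.5c: "Intervention process measures will be completed by randomized participants at the end of the first treatment and final (fifth) treatment sessions". The table headed "Table 8: Study variables and measurements gathered during the intervention" agrees: AAQ-II, CEQ, DBAS-10 and SHI are marked at sessions 1 and 5 only. The measure schedules for baseline, post-treatment and 3 months (Tables 7 and 9) list none of the four. The mailed short form described after section 3.4f holds only the ISI, PSQI and SF-12.

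**Reason.** Section 3.5c explains that "some measures cannot be completed until the individual has a basic understanding of the treatment program she will receive". The CEQ is the only measure to which this is then applied by name: "Since this measure cannot be used until the individual understands the type of treatment she will receive".

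**What comes before the first score.** In Table 10 the first ABC-I session covers personal values, the futility of controlling sleep, and an ACT exercise ("Leaves on a stream exercise"), besides sleep education, sleep hygiene and stimulus control. The introductory CBT-I session has the education, hygiene and stimulus-control parts without ACT.

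**Who reaches the last score.** Section 3.5b says the team "will consider an individual to have 'completed' treatment if they attend 5 60-minute sessions with the interventionist". Section 3.8c states: "we conservatively anticipate the dropout rate for ABC-I will be 22% compared to 45% for CBT-I". For women who stop treatment, section 3.8b says "we will continue to collect post-treatment and 3-month follow-up data, regardless of whether they complete the intervention program", but that collection does not include these three scales.

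**The concern.** The stated reason fits the CEQ: nobody can rate the credibility of a treatment she has not yet heard described. It does not explain why experiential avoidance, beliefs about sleep or sleep habits cannot be asked about before treatment starts. Two things follow.

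1. The earlier score is not a baseline. It follows a session whose ACT content is given in one arm only. If that content moves the AAQ-II or DBAS-10 in the intended direction, the arms already differ at the first measurement, and change from session 1 to session 5 leaves out part of the ABC-I effect. There is no pre-treatment score with which to check or correct this.
2. The later score depends on attending session 5. Treatment completion is a main outcome and is expected to differ by arm. Comparing session 5 scores between arms therefore compares two differently selected groups and is not a randomised comparison.

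At stake is what the trial can say about how the treatments work. The introduction to section 3.5 gives a better understanding of treatment process as one reason for the choice of measures.

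**Working it through.** **Inputs.** 74 women per arm; dropout 22% (ABC-I) and 45% (CBT-I), section 3.8c. Dropout range 16% to 28% for ABC-I and 39% to 51% for CBT-I, Table 11. Follow-up of 90%, from the earlier older-Veteran study cited in section 3.8b. Scale lengths 7, 10 and 13 items, section 3.5c. Projected enrolment 400 (Table 6) or 296 (section 3.3d), with 148 randomised.

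**Step 1: reproduce the plan's sample size.** This confirms which dropout rates the design rests on. With a two-sided 5% level (assumed, since Aim 1 states none) and 80% power:

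- Uncorrected n per arm = [1.960 × √(2 × 0.335 × 0.665) + 0.842 × √(0.22 × 0.78 + 0.45 × 0.55)]² / 0.23² = 64.9, i.e. 65.
- Continuity-corrected n = (64.9 / 4) × [1 + √(1 + 4 / (64.9 × 0.23))]² = 73.4, i.e. 74.
- Total 148, matching Table 11. The figure of 178 that section 3.8c also prints for this pair is the Table 11 entry for 24% versus 45%.

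**Step 2: women with a session 5 score.**

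| | ABC-I | CBT-I | Both |
|---|---|---|---|
| Expected score | 74 × 0.78 = 57.7 | 74 × 0.55 = 40.7 | 98.4 of 148 |
| Expected missing | 74 × 0.22 = 16.3 | 74 × 0.45 = 33.3 | 49.6 (33.5%) |

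At the corners of Table 11, overall missingness runs from (16% + 39%) / 2 = 27.5% to (28% + 51%) / 2 = 39.5%. Women who never attend session 1 have no score at all.

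**Step 3: precision.** If the post-treatment visit reached 90%, 148 × 0.90 = 133 women would have an end score, about 67 per arm. The standard error of a difference in means is proportional to √(1/n₁ + 1/n₂):

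- session 5 schedule: √(1/58 + 1/41) = 0.204
- assessment visit: √(2/67) = 0.173
- ratio 1.18, so about 18% larger under the present schedule.

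**Step 4: selection, as an illustration only.** Suppose there is no treatment effect on a scale, and that a normally distributed tendency to stay in treatment correlates ρ with the score, equally in both arms. Completers' mean then shifts by ρ × φ(c) / (1 − p), where p is the dropout rate, c its normal quantile and φ the normal density. The factor is 0.380 at p = 0.22 and 0.720 at p = 0.45. The spurious difference between arms is 0.340ρ: 0.03 SD at ρ = 0.1, 0.10 SD at ρ = 0.3 and 0.17 SD at ρ = 0.5. The documents give no value for ρ.

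**Step 5: is the first score contaminated?** No arithmetic applies, so each scale is set against Table 10.

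- AAQ-II: ABC-I delivers ACT content before the first form and CBT-I does not. The concern is strongest here.
- DBAS-10: section 3.5c says it covers beliefs about needing to control insomnia, which ABC-I takes up in session 1. In CBT-I the cognitive therapy comes in a later session. The concern is partial.
- SHI: it asks about habits, and the session 1 hygiene changes are set as homework, to be carried out after the form is filled in. The first score should be close to a pre-treatment one, although advice just heard could colour the answers.

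**The case against.** The strongest reply is that no planned analysis depends on these scales. Table 8 ties attendance and diaries to Aim 1 but gives the process measures no aim. Section 3.8 tests dropout, diary adherence, ISI, PSQI and actigraphic sleep percent. It specifies no mediation or change-score analysis, and only the CEQ has a stated comparison between arms, described as exploratory. The ACT content is there to improve adherence, which is measured directly. This stands, and it limits the weight of the point.

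A reader might infer three stronger things that the documents do not support:

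- That the main conclusions are compromised. They are not; Hypotheses 1 to 3 do not use these scales.
- That change in psychological flexibility will be understated. It may be. Nothing in the plan shows that one introductory session moves the AAQ-II, or by how much.
- That all three scales are equally affected at session 1. For the SHI the argument is weak.

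Two further objections are fair. The 90% reach comes from older Veterans, a different population, so the 18% is conditional on it. And moving the scales to baseline adds burden for women who are never randomised.

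The reply leaves the dependence of the last score on completion untouched. Section 3.8b provides multiple imputation for hypothesis testing but does not say that it extends to these scales. If it did, it would have to fill about a third of the end scores, unevenly by arm, with no pre-treatment score on the scale as a predictor.

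**Conclusion.** The point holds as a limit on process findings. As scheduled, the three scales have no pre-treatment score, and about 98 of 148 women would have an end score (78% of ABC-I, 55% of CBT-I). This assumes that the planned dropout rates hold and that session 5 forms come essentially only from women who count as completers. Any end-of-treatment comparison between arms would be conditional on completion. Change from session 1 to session 5 may understate the ABC-I effect on the AAQ-II, and less so on the DBAS-10; the size of any such shift is unknown. The gain in precision from moving the end score is about 18% in standard error if 90% can be reached, and less if reach is lower. It is a cheap improvement worth making, but not an error in the trial's main tests.

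**What to change.** Give the AAQ-II, DBAS-10 and SHI at the baseline assessment before randomisation, and again at the post-treatment assessment visit, by the blinded assessment staff, to all randomised women whether or not they complete treatment. The 3-month visit can be optional. Keep the CEQ at the end of sessions 1 and 5. Amend Tables 8 and 9 and section 3.5c to match.

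The cost is 7 + 10 + 13 = 30 short items at visits that already take place, partly offset by shorter sessions 1 and 5. The offset does not reach enrolled women who are not randomised: 296 − 148 = 148 or 400 − 148 = 252 of them, on the plan's two projections. If that burden is judged too high, a smaller change is to give the AAQ-II and DBAS-10 after randomisation but before session 1 begins, and again at the post-treatment visit. That spares the women who are not randomised, but a participant may by then know her allocation.

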3.6. Interventions

For both the ABC-I and CBT-I programs, materials are designed and tailored for women Veterans. Examples used will be directly geared toward the target population. In the ABC-I program, issues specific to women's sleep including changes in sleep associated with menopause and the menstrual cycle will be incorporated into the "sleep education" portion of the programs. Interventionists (ABC-I and CBT-I) will be trained to frequently pause to check participant understanding and treatment sessions will be designed to be interactive to facilitate participant engagement. Each session will begin with an outline of what will be discussed and end with a summary of the topics reviewed. At the conclusion of each session, a written outline of what was discussed with the specific, individualized recommendations written down in clear language will be provided to the participant.

3.6a. The ABC of Insomnia (Acceptance and the Behavioral Changes to treat Insomnia - ABC-I): The ABC-I program will involve 5 weekly sessions of 60 minutes each with the study interventionist (see **Table 10**). Sessions will incorporate the key components of sleep restriction, stimulus control and targeted sleep hygiene

recommendations. In place of specific or traditional cognitive therapy exercises, we will incorporate select exercises and strategies targeting each of the six essential components of Acceptance and Commitment Therapy (ACT). The added exercises and concepts were designed specifically to improve adherence to the behavioral components of insomnia treatment. Each exercise is introduced to preempt expected obstacles to adherence introduced in that session. For example, metaphors are introduced to describe temporary discomfort (e.g., home renovation) alongside introduction of a regular sleep schedule and reduced time in bed.

Appendix 5 shows the patient materials for Session 1 currently used at the UCSD Moores Cancer Center. Throughout treatment, participants will be asked to complete a daily sleep diary. We developed and tested a sleep diary in our HSR&D funded pilot study, and had an excellent rate of completion (105 out of 107 women completed the diary at least 5 out of the 7 nights). At each session, the diary will be reviewed and discussed. It will be used as a tool for refining treatment recommendations and adjusting each week's action plan.

3.6b. Cognitive-Behavioral Therapy for Insomnia (CBT-I) Program: The ABC-I program will be compared to CBT-I, provided in the same format to control for non-specific aspects of the ABC-I program and to evaluate the comparative effectiveness of the two treatments (see **Table 10**). Participants will maintain the same daily sleep diary throughout the treatment. The sleep restriction, stimulus control and sleep hygiene components will be analogous to what is provided within the ABC-I. The CBT-I program will also involve 5 60-minute meetings with the interventionist. In place of mindfulness and ACT-based exercises, cognitive therapy exercises and techniques will be utilized.

Table 10: ABC-I and CBT-I treatments: Session-by-session content, activities and homework

	Topics covered	Session activities	Homework
Session 1	ABC-I: Learning How to Surf: An introduction to the ABC of Insomnia program (sleep education, sleep hygiene and stimulus control + ACT; see Appendix 3)		
	
 Enhance motivation to adhere to behavioral prescriptions (values) Futility of trying to control sleep Sleep education: insomnia (3P model), sleep stages and macrostructure among women Lifestyle habits that enhance or hinder sleep among women Introduce and explain daily sleep diary 	
 Insomnia and what is important to you Metaphors: Chinese finger trap; surfing Leaves on a stream exercise Action plan: sleep hygiene changes; stimulus control 	
 Draw life with and without insomnia Implement action plan (sleep hygiene practices) Daily sleep diary
Session 2	CBT-I: Getting Started with CBT-I (sleep education, sleep hygiene and stimulus control)		
	
 Sleep education: sleep regulation, insomnia (3P model), sleep stages and macrostructure Introduce stimulus control concepts Lifestyle habits that enhance or hinder sleep Introduce and explain daily sleep diary 	
 Discuss classical conditioning and insomnia Action plan: sleep hygiene changes; stimulus control 	
 Implement action plan (sleep hygiene practices) Detailed daily sleep diary
Session 3	ABC-I: Renovating your Home (sleep restriction therapy + ACT)		
	
 Learn about the homeostatic and circadian sleep processes (sleep regulation) The rationale behind sleep restriction Discussion of short-term discomfort for long-term benefits 	
 Review/discussion of sleep diary Introduction of key metaphors: pizza dough, silly putty; piggy bank; hiking; home renovation Action plan: daily sleep schedule 	
 Implement action plan (sleep schedule) Daily Sleep diary
Session 4	CBT-I: Scheduling Sleep (sleep restriction therapy)		
	
 Learn about the homeostatic and circadian sleep processes The rationale behind sleep restriction 	
 Review/discussion of sleep diary Action plan: daily sleep schedule 	
 Implement action plan (sleep schedule) Daily sleep diary
Session 5	ABC-I: Taking Your Mind for a Walk (ACT exercises)		
	
 Adjust time in bed Understand the concept of dirty vs. clean discomfort Experience cognitive diffusion 	
 Review/discussion of sleep diary Troubleshooting techniques: physicalizing and visualization Take your mind for a walk Two scales metaphor Action plan: revise sleep schedule 	
 Implement action plan (sleep schedule) Use troubleshooting techniques as needed Daily sleep diary
Session 5	CBT-I: Thoughts about Sleep (cognitive therapy)		
	
 Adjust time in bed Discuss validity of sleep-related thoughts Discuss utility of sleep-related thoughts 	
 Review/discussion of sleep diary Develop coping cards Action plan: revise sleep schedule 	
 Implement action plan (sleep schedule; coping cards) Daily sleep diary
Session 4	ABC-I: Acceptance & Commitment (ACT exercises)		
	
 Adjust time in bed Review progress and challenges 	
 Review/discussion of sleep diary Addressing barriers and obstacles Action plan: new ways to face obstacles 	
 Implement action plan (sleep schedule; strategies to address obstacles) Daily sleep diary
Session 5	CBT-I: Progress and Obstacles (cognitive therapy)		
	
 Adjust time in bed Review progress and obstacles Use cognitive strategies to address barriers to adherence 	
 Review/discussion of sleep diary Addressing barriers and obstacles using cognitive-therapy methods Action plan: identify obstacles and strategies to address them 	
 Implement action plan (sleep schedule; strategies to address obstacles) Daily sleep diary
Session 5	ABC-I: If Not Tonight, Tomorrow Night (relapse prevention + ACT)		
	
 Adjust time in bed Understand relapse prevention techniques 	
 Review/discussion of sleep diary Action plan for relapse prevention 	
 Use tools/skills for future sleepless nights
Session 5	CBT-I: Sleeping Well Over the Long-Term (relapse prevention)		
	
 Adjust time in bed Discuss relapse prevention and coping 	
 Review/discussion of sleep diary Action plan for relapse prevention 	
 Use tools/skills for future sleepless nights

3.7. Data management:

Each participant will be assigned a unique ID which will be entered into computerized files and used on study forms. Only the ID number will be linked to participant data in databases and on paper documents. Using existing protocols, we will secure all paper records and electronic data files in compliance with current VA data security policies. Original study forms will be archived and stored in locked cabinets in approved research areas. All data will be coded by the data manager, then entered into databases using procedures established in prior work to minimize errors. Datasets will be cleaned by screening for out-of-range values, and comparing a random sample of 10% of entered data to original data collection forms. Problems with data entry will be addressed in an ongoing manner. Double entry procedures will be used on a second, 10% random sample of cases in each dataset, with additional training and review of data if errors are identified. Cleaned data will be scored and aggregated, then data will be merged into one main database for statistical analyses.

